5.3.5.2 Clinical Protocol

Table 3: Dose Limiting Toxicity Definition and Criteria

Toxicity Category	Drug-Related Toxicity/Grade
Hematologic	Grade 4 neutropenia for ≥ 5 days
	Febrile neutropenia: grade 4 neutropenia with fever > 38.5 °C both sustained over a 24 hour period.
	Neutropenic infection: grade ≥ 3 neutropenia with grade ≥ 3 infection
	Anemia \geq grade 4
	Grade > 4 thrombocytopenia or grade ≥ 3 thrombocytopenia and grade ≥ 3 hemorrhage
Nonhematologic	Grade 3 or 4 nonhematologic toxicity with the following exceptions: 
 • Nausea, vomiting or diarrhea for < 48 hours^a • Asymptomatic electrolyte abnormalities that are corrected to grade 1 or better in < 72 hours^b • headache lasting less than 48 hours

^aPatients with related grade 3 or 4 diarrhea, nausea or vomiting for ≥ 48 hours despite optimal medical therapy will require a one-level dose-reduction of TRC105.

^bPatients with related grade 3 or 4 electrolyte abnormalities that persist for ≥ 72 hours will require a one level dose-reduction of TRC105.

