5.3.5.2 Clinical Protocol

weeks (i.e., from cycle 2 day 1 through cycle 2 day 28). At least 6 patients will be treated at the every two week dosing MTD (or top dose level if a MTD is not determined).

Three patients will be initially enrolled and treated at each dose level. If none of these 3 patients experiences a dose-limiting toxicity (DLT) during the 28-day DLT evaluation period, dose escalation will proceed following review of safety data with site staff including the principal investigators at all sites.

If 1 of 3 patients experiences DLT, the dose level will be expanded to 6 patients. The maximum tolerated dose (MTD) will have been exceeded if $\geq 33\%$ of patients experience DLT at a given dose level. DLT will have occurred when a patient has 1 or more toxicity listed in the table below that is at least possibly related to the combination of pazopanib and TRC105 during the 28 day DLT evaluation period. Patients who exit the study for reasons other than DLT or any TRC105 dose delay >2 days in cycle 2 prior to completion of the 28-day DLT evaluation period will be replaced to ensure an adequate safety assessment in each cohort. Patients who experience DLT who receive less than the prescribed dose of TRC105 or pazopanib due to documented toxicity during the DLT evaluation period will be considered evaluable for dose escalation purposes. A given TRC105 dose level may be reenrolled at $\geq 50\%$ of the pazopanib dose intensity upon agreement of study investigators.

Toxicity Category	Drug-Related Toxicity/Grade
Hematologic	Grade 4 neutropenia for ≥ 5 days
	Febrile neutropenia: grade 4 neutropenia with fever > 38.5 °C both sustained over a 24 hour period.
	Neutropenic infection: grade ≥ 3 neutropenia with grade ≥ 3 infection
	Anemia \geq grade 4
	Grade > 4 thrombocytopenia or grade ≥ 3 thrombocytopenia and grade ≥ 3 hemorrhage
Nonhematologic	Grade 3 or 4 nonhematologic toxicity with the following exceptions: 
 Nausea, vomiting or diarrhea for < 48 hours^a Asymptomatic electrolyte abnormalities that are corrected to grade 1 or better in < 72 hours^b headache lasting less than 48 hours

^aPatients with related grade 3 or 4 diarrhea, nausea or vomiting for ≥ 48 hours despite optimal medical therapy will require a one-level dose-reduction of TRC105.

^bPatients with related grade 3 or 4 electrolyte abnormalities that persist for ≥ 72 hours will require a one-level dose reduction of TRC105.

Phase 2:

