5.3.5.2 Clinical Protocol

2.2.1.2. Phase 1b 105ST102 Study with Bevacizumab

2.2.1.2.1. 105ST102 Summary of Safety

Administration of TRC105 at a dose of 3 mg/kg weekly in combination with bevacizumab was well tolerated by three patients without the development of dose limiting toxicity (DLT) and dose escalation occurred per the protocol to cohort 2 (6 mg/kg TR105 weekly). However, the concurrent administration of 6 mg/kg TRC105 and bevacizumab on day 1 resulted in the development of moderate or severe headaches (including two grade 3 headaches) in four of five treated patients. The 6 mg/kg dose of TRC105 was tolerated when the initial TRC105 dose was delayed one week following bevacizumab dosing at 10 mg/kg every two weeks. Tolerability was further improved when the initial dose of TRC105 was given over two days during the first week of TRC105 dosing, and dose escalation proceeded to the recommended phase 2 dose of 10 mg/kg TRC105 weekly. At the recommended phase 2 dose of both drugs (10 mg/kg), TRC105 serum concentration were present above target concentration continuously and immunogenicity was rarely observed.

A total of 38 patients were dosed on study across six cohorts and four dose levels. Other than headaches that were mitigated by adjusting the dosing schedule of TRC105, the combination of TRC105 and bevacizumab was well tolerated. Two patients experienced grade 3 serious adverse suspected events as described below. Most adverse events were graded as 1 or 2 and Grade 4 and 5 suspected adverse events were not observed. Grade 3 suspected adverse reactions included anemia (the dose limiting toxicity of TRC105 established as a single agent; 9 patients), headache (4 patients; three of which occurred prior to adjusting the schedule of TRC105), fatigue (2 patients), brain abscess (1 patient), infusion reaction (in a patient dosed at 6 mg/kg), and decreased appetite (1 patient). Headache was the most common suspected adverse event and occurred in 31 patients (86.1%); three patients (7.9%) experienced migraine headaches (two of grade 1 and one of grade 2 severity). Headaches were treated with triptans and NSAIDs.

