5.3.5.2 Clinical Protocol

angioedema, asthenia, throat irritation, rhinitis, vomiting, joint pain, fatigue and neurologic disorders including inflammation of the spine and/or brain.

Hypersensitivity reactions with infusions are a potential risk for sensitized patients, and TRC105 should be used with caution in patients with known hypersensitivity to any component of the drug product. Host anti-TRC105 antibodies to the murine or human portions of CHO-produced TRC105 are rare. In general, the risk of immunogenicity to therapeutic chimeric antibodies is small (<10%) and the clinical significance of immunogenicity is not well defined. The current trial will collect serial blood samples for anti-product antibody concentrations to further characterize the immunogenicity of TRC105 and potential clinical implications.

Grade 3 cerebrovascular hemorrhage resulting in hemiparesis occurred in one patient with hepatocellular cancer who was thrombocytopenic (who entered the study with a platelet count of 60,000/uL) in a study of TRC105 with sorafenib. Patients must have a platelet count of > 100,000/uL to enter this study (see inclusion criteria). A grade 2 transient ischemic attack was reported in a study of TRC105 and pazopanib. Transient Grade 3 hepatic encephalopathy occurred in one patient with cirrhosis and hepatocellular carcinoma who received TRC105 in combination with sorafenib. Grade 3 pancreatitis was also observed in this study. Grade 5 intracranial hemorrhage occurred in one glioblastoma patient with markedly abnormal blood clotting parameters in a study of TRC105 with bevacizumab. A patient with glioblastoma developed temporary confusion and slurred speech following treatment with TRC105 and bevacizumab that required hospitalization for observation. Another patient with glioblastoma, who underwent resection and had a history of an abnormal collection of cerebral spinal fluid, developed a grade 2 cerebral spinal fluid leak. A third patient with glioblastoma with a history of recurrent meningitis developed recurrent grade 3 bacterial meningitis while treated with bevacizumab and TRC105.

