Grade 3 myocardial infarction (non-Q wave infarct associated with hypertension following an infusion reaction) was observed in a patient with hepatocellular cancer following treatment with TRC105 that resolved without sequelae. In addition, a Grade 5 myocardial infarction occurred in a patient with coronary artery disease who received TRC105 in combination with sorafenib. Patients with evidence of active coronary artery disease are excluded from participation in this trial (see exclusion criteria).

Adult respiratory distress syndrome that required temporary intubation occurred in one patient who received TRC105 with pazopanib, from which the patient recovered. Of note, interstitial lung disease has been added as an adverse drug reaction and warning/precaution to the core safety information for pazopanib. Pneumothorax (collapsed lung) has been observed in trials of TRC105 administered with VEGF inhibitors in patients with lung metastases. In addition, pneumothorax was observed in one patient, also with lung metastases, receiving single-agent TRC105.

Infections have been observed rarely. Grade 3 infected lipoma/cyst was observed in a Phase 2 study of TRC105 as a single agent in patients with metastatic bladder cancer. Grade 3 orbital cellulitis and grade 3 brain abscess were observed in patients treated with TRC105 and bevacizumab and considered possibly related to TRC105. Grade 1 and 2 gingivitis including infection and ulceration has also been observed. Overall, infections have been observed in fewer

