Three patients will be initially enrolled and treated at each dose level. If none of these 3 patients experiences a dose-limiting toxicity (DLT) during the 28-day evaluation period (extending from cycle 2 day 1 until cycle 2 day 28), dose escalation will proceed following review of safety data with site staff including the principal investigators at all sites.

If 1 of 3 patients experiences DLT, the dose level will be expanded to 6 patients. The maximum tolerated dose (MTD) will have been exceeded if $\geq 33\%$ of patients experience DLT at a given dose level. DLT will have occurred when a patient has 1 or more toxicity listed in the table below that is at least possibly related to the combination of pazopanib and TRC105 during the 28 day DLT evaluation period (cycle 2). Patients who exit the study for reasons other than DLT prior to completion of the 28-day DLT evaluation period (cycle 2) will be replaced to ensure an adequate safety assessment in each cohort. Patients who experience DLT who receive less than the prescribed dose of TRC105 or pazopanib due to documented toxicity during the DLT evaluation period will be considered evaluable for dose escalation purposes. A given TRC105 dose level may be reenrolled at $\geq 50\%$ of the pazopanib dose intensity upon agreement of study investigators.

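### The DLT tables list nonhematologic toxicity at grades 3 and 4 only, so a related nonhematologic event recorded solely as grade 5 in cycle 2 is not a DLT as written

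*Combined protocol and SAP*

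**What the plan says.** Section 4.1.1.1 (Phase 1b Overview) ties the definition to the table: "DLT will have occurred when a patient has 1 or more toxicity listed in the table below", provided the toxicity is at least possibly related and falls in the 28-day window (cycle 2). The synopsis has the same rule. In both the synopsis table and Table 3, the nonhematologic row is "Grade 3 or 4 nonhematologic toxicity with the following exceptions". The exceptions are short-lived gastrointestinal symptoms, electrolyte abnormalities and headache.

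Grade 5 is a separate grade in this trial: Table 16 defines it as fatal, and Section 8.2.2 uses it for deaths.

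On replacement, Section 4.1.1.1 says: "Patients who exit the study for reasons other than DLT prior to completion of the 28-day DLT evaluation period (cycle 2) will be replaced".

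The MTD is exceeded when at least 33% of patients at a dose level have a DLT (Section 4.1.1.1). Section 10.1.1 defines the estimated MTD as the highest tested level with a rate below 33% in at least 6 evaluable patients. Section 6.1.2.2 makes every-two-week dosing in phase 2 conditional on that MTD not being exceeded and on notification by the sponsor.

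**The concern.** Read literally, the row counts a grade 3 or grade 4 myocardial infarction but not one whose only record is grade 5. No safety rationale supports that, and the rest of the table suggests it was not intended. Anemia counts from grade 4 upward. Infection with neutropenia, and hemorrhage with thrombocytopenia, count from grade 3 upward. All three take in grade 5.

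The replacement rule could add to the gap. A patient whose fatal event is not a listed DLT could be treated as having left for another reason and be replaced, which would remove the event from both numerator and denominator.

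At stake is the DLT count for dose level 3 and expanded cohort 2, the part of phase 1b still open. That count feeds the decision on giving 15 mg/kg every two weeks to phase 2 patients. Section 2.5.1 shows that fatal nonhematologic events have occurred with TRC105 plus other agents: "Grade 5 intracranial hemorrhage occurred in one glioblastoma patient with markedly abnormal blood clotting parameters in a study of TRC105 with bevacizumab", and "a Grade 5 myocardial infarction occurred in a patient with coronary artery disease who received TRC105 in combination with sorafenib".

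**Working it through.** **1. The plan's own figure.** Table 17 gives the probability of escalating under 3+3. With true rate p of counted DLTs, it is (1−p)³ + 3p(1−p)² × (1−p)³. At p = 10% this is 0.729 + 0.177 = 0.906, against 0.91 in the table. For rates of 5% to 90% the formula gives 0.973, 0.906, 0.709, 0.494, 0.309, 0.172, 0.082, 0.032, 0.009 and 0.001, which agree with Table 17. The table depends only on the rate of events that count, so it neither reveals the gap nor changes with the fix.

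**2. What is and is not listed (related events, cycle 2).**

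| Event | Listed? |
|---|---|
| Anemia, grade 4 or 5 | Yes |
| Grade 5 infection with grade ≥ 3 neutropenia | Yes |
| Grade 5 hemorrhage with grade ≥ 3 thrombocytopenia | Yes |
| Nonhematologic, grade 3 or 4 recorded, then grade 5 | Yes, through the grade 3 or 4 record (Section 8.3.9 records each grade change as a new event) |
| Other nonhematologic, recorded only as grade 5 | No |

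**3. The threshold.** With the minimum of 6 evaluable patients, 1/6 = 16.7% is below 33% and 2/6 = 33.3% is above it, so one uncounted event can change the decision.

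**4. How often that would happen.** Let p be the rate of listed DLTs and u the rate of unlisted fatal events, with such patients kept in the denominator. The decision changes when there are fewer than 2 listed DLTs but at least 2 events in all. Its probability is g(p+u) − g(p), where g(q) = 1 − (1−q)⁶ − 6q(1−q)⁵.

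Inputs:
- p from 5% (assumed) to 15.3%. The upper end is the one-sided 95% bound from no DLT in 18 patients (Section 2.2.1.4): 1 − 0.05^(1/18) = 0.153. Those patients were on weekly dosing, so applying the bound to the every-two-week schedule is an assumption.
- u is not given in the documents; 0.1% to 1% is assumed.

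| p | u = 0.1% | u = 1% |
|---|---|---|
| 5% | 0.0340 − 0.0328 = 0.0012 | 0.0459 − 0.0328 = 0.0131 |
| 10% | 0.1162 − 0.1143 = 0.0020 | 0.1345 − 0.1143 = 0.0202 |
| 15.3% | 0.2330 − 0.2306 = 0.0024 | 0.2544 − 0.2306 = 0.0238 |

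At u = 0 the probability is 0. If these patients are replaced instead, the printed rule sees a rate of p/(1−u), and the values at u = 1% are 0.013, 0.018 and 0.020, so the order of magnitude does not change.

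**The case against.** The strongest reply is that the gap matters only under a very literal reading. It needs an event that is related, nonhematologic and fatal within 28 days, with no grade 3 or 4 stage recorded. Escalation follows a safety review with the principal investigators (Section 4.1.1.1), in-house and external safety review teams operate (Section 8.4), and every-two-week dosing in phase 2 also needs sponsor notification. A related death would have to be disregarded at each step. The replacement rule is meant to secure an adequate safety assessment, which argues against using it to discard a drug-related death.

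The two fatal cases also transfer poorly. This trial requires an INR of 0.8 to 1.2, excludes brain involvement unless treated and inactive, and excludes angina or infarction within 6 months (Sections 5.1 and 5.2). In 105ST102, the bevacizumab combination study with 38 patients, "Grade 4 and 5 suspected adverse events were not observed".

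All of this stands and keeps the effect small. It does not alter the written rule: those safeguards would work here only by departing from the definition.

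A reader might infer three stronger points that the documents do not support:

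- **Thrombocytopenia.** The row reads "Grade > 4 thrombocytopenia or grade ≥ 3 thrombocytopenia and grade ≥ 3 hemorrhage", which suggests that isolated grade 4 thrombocytopenia is also omitted. The text was read from PDF, and it cannot settle whether the source prints > or ≥. No claim is made about that row.
- **A larger effect.** No events in 38 patients gives an upper bound of 1 − 0.05^(1/38) = 7.6%, which might be used as the unlisted rate. That bound covers all grade 4 and 5 events, including grade 4 nonhematologic events that already count as DLTs, so it does not measure this gap.
- **Dose delays.** The synopsis replacement sentence refers to "Patients who exit the study for reasons other than DLT or any TRC105 dose delay >2 days in cycle 2", which can be read two ways. It supports no conclusion about patients held for a delay.

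**Conclusion.** The point holds in a narrow form. The DLT definition is confined to the table, the nonhematologic row stops at grade 4, and nothing elsewhere adds a related death. This is an incorrect rule as written, since it departs from the open-ended rows of the same table.

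The practical effect is small: about 0.1% to 2.4% of MTD decisions with 6 patients. This assumes an unlisted rate of 0.1% to 1% and a listed DLT rate of 5% to 15.3%, and that the literal rule is applied despite the safety reviews. A reader might go on to infer that a completed result is compromised. The documents do not show that: they report no DLT in the 18 patients at 8 and 10 mg/kg weekly, and the remaining exposure is confined to dose level 3 and expanded cohort 2.

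**What to change.** In the nonhematologic row of both the synopsis DLT table and Table 3, replace the reference to grades 3 and 4 with grade ≥ 3, and keep the list of exceptions as it is. Do this before dose level 3 DLTs are counted. A grade 5 event then counts as a DLT, and the patient no longer falls under the replacement rule for non-DLT exits. The cost is a short wording amendment in two places. It needs no extra patients or data and no change to Table 17.

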4.1.1.2. Phase 2 Overview

This is a multicenter, non-randomized, phase 2 study of TRC105 in combination with standard dose pazopanib. Sixty three patients will be treated in the phase 2 portion of the study at 10 mg/kg weekly; the MTD (top dose level studied as a MTD was not determined) of the phase 1b portion of the study (dose levels -1, 1, 2 and expanded cohort 1). Patients will receive pazopanib once daily and will receive TRC105 at 3 mg/kg on cycle 1 day 1, 7 mg/kg on cycle 1 day 4, and 10 mg/kg on cycle 1 day 8 and weekly thereafter. Each cycle is 28 days in duration.

Two additional phase 2 cohorts of up to thirteen patients each with angiosarcoma that have had disease progression following treatment with prior systemic therapy will be assessed.

Angiosarcoma cohort 1 patients will initially receive weekly single-agent TRC105 at a dose of 10 mg/kg weekly with transition to treatment with the combination of TRC105 and pazopanib at progression per RECIST 1.1.

Angiosarcoma cohort 2 patients will be assessed at a TRC105 dose of 10 mg/kg weekly in combination with 800 mg pazopanib once daily for the first cycle starting on cycle 1 day 1 followed by TRC105 15 mg/kg administered every two weeks starting from cycle 2 day 1 onward in combination with pazopanib 800 mg once daily.

Active patients that are past cycle 1, may be switched to an every 2 week dosing schedule at a TRC105 dose of 15 mg/kg every two weeks once **SPONSOR SENDS NOTIFICATION TO PROCEED WITH EVERY TWO WEEK DOSING.**

- TRC105 will be administered at 10 mg/kg weekly during cycle 1.

5.3.5.2 Clinical Protocol

- The first weekly TRC105 dose (10 mg/kg) will be split into two doses whereby 3 mg/kg is administered on cycle 1 day 1 and the balance is administered on cycle 1 day 4.
- Starting on cycle 2 day 1 and beyond, TRC105 may be administered every two weeks on days 1 and 15 at the every two week dosing MTD.

Pazopanib dosing will start at 800 mg once daily. Dose reductions of pazopanib are allowed based on individual patient tolerability. Each cycle in this cohort is 28 days in duration.

4.1.2. Trial Procedures

All on-study procedures are permitted within the time window indicated in the Schedule of Assessments ([Table 4](#), [Table 5](#), [Table 6](#) and [Table 7](#)).

4.1.2.1. Screening

The following screening procedures must be performed within 28 days prior to the first day of study therapy. Qualifying hematology (including Fe studies), serum chemistry (including TSH testing), coagulation, physical examination, ECG, pregnancy and urinalysis collected within 7 days of cycle 1 day 1 do not need to be repeated. The following will be performed according to the Schedule of Assessments ([Table 4](#), [Table 5](#), [Table 6](#) and [Table 7](#)).

- Patient signature on current Institutional Review Board (IRB) approved informed consent form. Prior to undergoing any study-specific procedure, patients must read and sign the current Institutional Review Board (IRB) approved informed consent form. Patients may sign consent prior to the 28 day screening period.
- Medical history, baseline signs and symptoms, prior cancer therapy, prior cancer surgery, prior radiation therapy, drug allergies, primary diagnosis and demographics.
- Physical examination including examination of all major body systems, ECOG performance status, and vital signs.
- Hematology (including serum iron, ferritin and total iron binding capacity), coagulation (INR) and serum chemistry (including thyroid stimulating hormone (TSH)) to be performed locally.
- Serum or urine pregnancy test for all females of childbearing potential to be performed locally.
- Urinalysis to be performed locally. Microscopic analysis and/or urine protein-creatinine ratio (UPCR) should be performed as clinically indicated.
- CT or MRI scans of chest, abdomen and pelvis in addition to any other applicable sites of disease. Brain and bone scans to be performed if metastasis is suspected prior to starting the study. Color photography with caliper or ruler measurements should be used to assess cutaneous tumors (target lesions).
- Single tracing 12-Lead ECG (QT, PR and QRS intervals and heart rate will be captured).
- Assessment of concomitant medications and treatments from 28 days prior to the start of study treatment.

5.3.5.2 Clinical Protocol

- Archival Tumor Tissue Specimens: Archival specimens (formalin-fixed, paraffin-embedded) of the primary cancer specimen and/or metastatic cancer specimen for each study participant. It is preferable that the entire paraffin block be submitted, but if this is not feasible, then at least 20 unstained slides are requested for immunohistochemical analysis (sections of ~ 5 microns are preferred). See separate laboratory guide for further collection and shipment information.

4.1.2.2. Trial Period

Qualifying hematology (including Fe studies), blood chemistry (including TSH testing), coagulation, urinalysis, physical examination, ECG, and pregnancy test do not need to be repeated on cycle 1 day 1 if acceptable screening assessments are performed within 7 days prior to the start of study therapy. For dose levels -1, 1, 2 and expanded cohort 1 of the phase 1b portion of the study, prior to administration of TRC105 on cycle 2 day 1, all study patients must maintain eligibility criteria indicating adequate organ function, medical status and ECOG performance status (i.e., all patients must maintain inclusion criterion #4, 5 and 6 and exclusion criteria #8-21 to continue into cycle 2). On days of dosing, all assessments should be performed prior to dosing with TRC105 unless otherwise indicated in the Schedule of Assessments. Patients will receive 2 cycles (approximately 6-8 weeks) of treatment. Patients who demonstrate a response of CR, PR or SD, will be eligible for additional treatment until progression. For patients in the angiosarcoma cohort 1, disease progression for withdrawal from study therapy refers to disease progression while receiving TRC105 plus pazopanib combination therapy. Patients who cannot tolerate pazopanib or TRC105 therapy and who demonstrate a response of complete response (CR), partial response (PR) or stable disease (SD) with the combination and are thought to benefit from continued single agent therapy may continue on study on TRC105 or pazopanib alone. Each cycle is 28 days in duration, with the exception of cycle 1 for phase 1b dose levels -1, 1, 2 and expanded cohort 1 which will be 2 to 4 weeks in duration. The following will be performed according to the Schedule of Assessments ([Table 4](#), [Table 5](#), [Table 6](#) and [Table 7](#)).

- Physical examination including examination of all major body systems, ECOG performance status, weight and vital signs (heart rate, temperature, blood pressure, respiratory rate).
 - Assessment of vital signs during TRC105 infusion: Vital signs are to be assessed pre-infusion (i.e., within 30 minutes of starting the infusion), every 30 minutes during the infusion (+/- 15 minutes), and at the end of the infusion (i.e., within 30 minutes after completing the infusion). Vital signs should be monitored more frequently and/or beyond the completion of the infusion if medically indicated (e.g. if the patient experiences an infusion reaction that has not yet resolved).
- Hematology, coagulation (INR) and serum chemistry (including TSH) to be performed locally.
- Serum or urine pregnancy test for all females of childbearing potential to be performed locally.
- Single tracing 12-Lead ECG (QT, PR and QRS intervals and heart rate will be captured).

